## **8.1 Statistical analysis of the primary efficacy variable**

The primary efficacy variable measurement for this study is based on ASDAS-MI response at Week 52. However, the primary outcome of the study will be defined as a composite endpoint that is achieved if a subject fulfills the following 2 components:

1. Remain in the study and on the double-blind study treatment through 52 weeks
2. Achieve an ASDAS-MI response at 52 weeks

For simplicity, this primary efficacy variable will be referred to as ASDAS-MI response at Week 52. However, the composite definition as described above will apply when this endpoint is analyzed.

### 8.1.1 Derivation of primary efficacy variable

The ASDAS is comprised of a number of assessments which are scored by the subject and physician and multiplied by a proven formula (van der Heijde et al, 2008) as listed:

- 0.121 x Back pain (BASDAI Q2 result)
- 0.058 x Duration of morning stiffness (BASDAI Q6 result)
- 0.110 x Patient's Global Assessment of Disease Activity (PGADA)
- 0.073 x Peripheral pain/swelling (BASDAI Q3 result)
- 0.579 x (natural logarithm of the (CRP [mg/L]+ 1))

Back pain, PGADA, duration of morning stiffness, peripheral pain/swelling and fatigue are all assessed on a numerical scale (0 to 10 units) (Lukas et al, 2009).

The sum of these weighted components gives the ASDAS.

If exactly 1 component for the ASDAS is missing at a given visit, that component will be imputed by LOCF, and the ASDAS will be calculated accordingly. If more than one component for the ASDAS is missing, ASDAS will be treated as missing.

For CRP values below the lower limit of quantification (<4mg/L), half the lower limit (2mg/L) will be used as the imputed value.

Disease activity categories based on ASDAS are as follows:

- ASDAS-Inactive Disease (ASDAS-ID): ASDAS <1.3
- ASDAS-Moderate Disease (ASDAS-MD\*)/ASDAS-Low Disease (ASDAS-LD): ASDAS  $\geq 1.3$ , <2.1  
\* ASDAS-MD is equivalent to ASDAS-LD. Whereas protocol amendment 5 uses ASDAS-LD throughout the SAP and Shells will continue to use ASDAS-MD in order to maintain consistency with the double-blind TFLs previously produced for this study.
- ASDAS-High Disease Activity (ASDAS-HD): ASDAS  $\geq 2.1$ ,  $\leq 3.5$
- ASDAS-very High Disease Activity (ASDAS-vHD): ASDAS >3.5

Note that ASDAS-MD (used in study protocol amendments 4 and earlier) is identical to the definition of ASDAS-LD used in the study protocol amendment 5. ASDAS-LD instead of ASDAS-MD is following an update of the nomenclature (Machado et al, 2018). ASDAS-MD is used throughout this SAP and in the analysis outputs in order to retain consistency with the Week 52 interim database lock analyses.

The variables related to ASDAS improvement are defined as follows:

- ASDAS-Clinically Important Improvement (ASDAS-CII): ASDAS reduction (improvement) of  $\geq 1.1$  relative to Baseline
- ASDAS-Major Improvement (ASDAS-MI): ASDAS reduction (improvement) of  $\geq 2.0$  relative to Baseline or has the lowest score possible post-baseline (i.e. when CRP < LLOQ and all other components are 0, then the minimum ASDAS score is 0.636 to 3 decimal places).  
Note: As a sensitivity analysis, the primary analysis will be repeated where ASDAS-MI includes the criteria ASDAS reduction (improvement) of  $\geq 2.0$  relative to Baseline only.

ASDAS-MI at 52 weeks is the primary variable for efficacy analysis.

### 8.1.2 Primary analysis of the primary efficacy variable

The primary analysis for of the primary efficacy variable will be based on logistic regression. The odds ratio of the ASDAS-MI responder rates at Week 52 will be estimated and tested between treatment groups using a logistic regression model with factors of treatment group, region, and MRI/CRP classification (MRI+/CRP+; MRI+/CRP-; MRI-/CRP+). The MRI/CRP classification used in all statistical analysis will be recalculated using source data as described in [Section 4.8](#) and the IXRS MRI/CRP categorization will not be used. If the logistic regression model is unable to converge, then the MRI/CRP classification variable may be dropped from the model to facilitate convergence. The study design is likely to result in some sites with a small number of enrolled subjects. The use of region as a factor in the model is intended to combine study centers in similar geographic regions. The geographic regions to be used will be as defined in the IXRS randomization system. In the unlikely event that a subject moves sites during the study which leads to a change in region, the region originally used at randomization will be used in the analysis.

Given the composite endpoint definition described in [Section 8.1](#), there will be no missing data for the primary endpoint, as subjects that discontinue double-blind study treatment prior to Week 52 or who do not have an ASDAS-MI response at Week 52 are considered non-responders to the double-blind study treatment.

Tables will present the responder rates for placebo and CZP 200mg, the respective effect estimates (adjusted odds ratio with reference to placebo), p-values, and 95% confidence intervals (CIs). The odds ratios and 95% CIs will also be presented graphically.

### 8.1.3 Supportive and sensitivity analyses of the primary efficacy variable

As described in [Section 6.3](#) of the protocol, subjects who discontinue study treatment will not necessarily be withdrawn from the study. In an attempt to minimize missing data, efforts will be made to continue to collect safety and efficacy data on these subjects through study completion. In order to assess the impact of various missing data assumptions on the analysis, four sensitivity analyses of the primary efficacy variable will be performed as described in [Section 4.2.1](#). Further details of these analyses are provided in this section. The odds ratios  $\pm$  95% CI's for the primary analyses and sensitivity analyses will be presented on the same graph to allow visual comparison of the robustness of the results. In addition, a summary of the missing data pattern will be provided.

For Canada (and any other country where applicable or where requested by Regulatory Authorities), the primary efficacy variable measurement is the ASAS40 response at Week 12. Analysis of the ASAS40 response at Week 12 will be performed as described above for

ASDAS-MI response at Week 52 (including all sensitivity and subgroup analyses). Similar to the ASADAS-MI efficacy endpoint, the primary analysis of ASAS40 will be treated as a composite endpoint when it is analyzed. Specifically, subjects will need to: 1) achieve the relevant response (ASAS40); and 2) remain in the study and on their randomized double-blind study treatment through Week 12.

In addition to the above analyses, subgroup summaries using descriptive statistics, estimates and confidence intervals only for the primary efficacy variable by age, gender, race, symptom duration, tobacco use, HLA-B27 genotype, region, prior anti-TNF exposure, Baseline SPARCC score ( $<5$ ,  $\geq 5$ ), subjects with/without relevant changes to background medication, and MRI/CRP classification (MRI+/CRP+; MRI+/CRP-; MRI-/CRP+) will be performed.

The logistic regression analyses of the composite endpoint for ASDAS-MI responder rates at Week 52 (as described in [Section 8.1.2](#)) will also be repeated using the PPS and the Randomized Set. In addition, the primary analysis will be repeated where ASDAS-MI includes the criteria ASDAS reduction (improvement) of  $\geq 2.0$  relative to Baseline only.

### 8.1.3.1 Including observed data at Week 52

The observed data at Week 52 will be used and analyzed according to randomized treatment, regardless of whether or not the subject is still on his/her randomized double-blind study treatment at that time. For example, subjects on OL-CZP or OL-OT at the time of their Week 52 visit will have that data included in the analysis including observed data at Week 52. Despite efforts to continue to collect data on all subjects (even if they discontinue the double-blind study treatment), there may still be subjects with missing data at Week 52. Such subjects will be considered as non-responders. The same logistic regression model specified for the primary analysis will be used. The odds ratio of the treatment comparison and corresponding 95% CI for ASDAS-MI responder rates at Week 52 based on the observed data will be estimated using a logistic regression model with factors of treatment group, region, and MRI/CRP classification (MRI+/CRP+; MRI+/CRP-; MRI-/CRP+).

### 8.1.3.2 Multiple imputation

Investigators will be given discretion to discontinue study treatment for subjects not responding in order to provide them with other treatments for the condition. Therefore, in many cases, missing efficacy data due to study treatment discontinuation should be dependent on the observed efficacy scores, but independent of unobserved data. This would be consistent with a missing at random (MAR) pattern of missingness. In order to investigate the efficacy results under the assumption of data being MAR, a multiple imputation method will be applied as follows:

1. The continuous ASDAS score at each visit will be calculated using the methods described in [Section 8.1.1](#) (including the application of LOCF if only one component is missing). Visits with more than one component missing will be set to missing. ASDAS data collected after the discontinuation of double-blind study treatment will be treated as missing in the original data set for this sensitivity analysis. Hence, all open-label period data is excluded from this analysis.
2. For subjects with a non-monotone (intermittent) missing pattern, MCMC will be used to impute their missing intermittent ASDAS scores including treatment arm, region, MRI/CRP

classification and ASDAS measurement from previous visit(s) as explanatory variables in the model. This will be done 100 times limiting the imputation to in range results.

After this step there will be 100 datasets containing all subjects however the only missing data will be a monotone missing data pattern. A variable called “\_imputation\_” will identify each of the 100 imputed datasets output.

3. The remaining missing data for all subjects with a monotone missing data pattern will be imputed using regression with treatment arm, region, MRI/CRP classification and ASDAS measurement from previous visit(s) as explanatory variables. This model will be run once for each of the imputed datasets limiting imputation to in range results.
4. The ASDAS change from Baseline to Week 52 will be calculated using the complete datasets (with no missing data) and categorized as: ASDAS-MI or not ASDAS-MI (as defined in [Section 8.1.1](#))
5. For each of the 100 imputed datasets (identified by \_imputation\_ variable), the odds ratio of the treatment comparison and corresponding 95% CI for ASDAS-MI responder rates at Week 52 based on the observed data will be estimated using a logistic regression model with factors of treatment group, region, and MRI/CRP classification (MRI+/CRP+; MRI+/CRP-; MRI-/CRP+) and Baseline as a covariate in the same manner as the primary endpoint analysis.
6. The results from these analyses will be combined into a single inference using SAS PROC MIANALYZE.

The parameter estimate and 95% CIs will be back transformed (using the exponential function) to give the odds ratio and CI for the CZP vs PBO comparison. This will be presented alongside the p-value from the proc mianalyze.

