#### 8.1.3.4 Observed case analysis

This analysis will only include the observed data for subjects still on the original double-blind study treatment. Subjects with missing ASDAS data at Week 52 will not be included in the

analysis and hence only a subset of subjects will be analyzed and no composite endpoint implemented. The same logistic regression model specified for the primary efficacy analysis will be performed. The odds ratio and corresponding 95% CI of the ASDAS-MI responder rates at Week 52 based on the observed data will be estimated and tested between treatment groups using a logistic regression model with factors of treatment group, region, and MRI/CRP classification (MRI+/CRP+; MRI+/CRP-; MRI-/CRP+).

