3. For each completed data set, the outcome (response or change from Baseline) will be calculated using the complete datasets (with no missing data).
4. For ASAS40, complete parts 5 and 6 from [Section 8.1.3.2](#) in order to provide odds ratios, 95% CIs and the p-value from the proc mianalyze. For BASDAI, BASFI, SI joint SPARCC, ASQoL and Nocturnal Spinal Pain, complete parts 4 and 5 from [Section 8.2.2.2](#) in order to provide treatment differences, 95% CIs and the p-value from the proc mianalyze.

Additionally, change from Baseline in SI joint SPARCC score at Week 12 is a continuous secondary efficacy variable. The same referenced based multiple imputation procedure specified in this section will be used to account for missing SPARCC data. However, it should be noted that, unlike BASDAI and BASFI, SPARCC score will not be measured at any time points between Baseline and Week 12, meaning that those are the only 2 time points that can be considered in the evaluation of SPARCC score at Week 12. Comparisons between treatment groups will be made using an analysis of covariance (ANCOVA) model on the imputed data set. The model will include Baseline score, treatment group, region, and MRI/CRP classification.

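### The multiple-imputation and tipping-point models add a Baseline covariate that the primary model lacks, so their odds ratios are not like-for-like with the primary

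*SAP*

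**What the plan says.** Section 8.1.2 estimates the primary odds ratio "using a logistic regression model with factors of treatment group, region, and MRI/CRP classification". It names no baseline covariate. Section 4.1 leaves covariates to be described with each analysis, and Section 8.1 describes none for the primary beyond these factors.

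Two of the four sensitivity analyses keep that model. Section 8.1.3.1 (observed data at Week 52) says: "The same logistic regression model specified for the primary analysis will be used". Section 8.1.3.4 (observed case) says: "The same logistic regression model specified for the primary efficacy analysis will be performed". The other two do not. Section 8.1.3.2 step 5 lists the same three factors and then adds "and Baseline as a covariate in the same manner as the primary endpoint analysis"; Section 8.1.3.3 step 4 repeats the addition in the same words.

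Section 8.1.3 gives the purpose: "In order to assess the impact of various missing data assumptions on the analysis, four sensitivity analyses of the primary efficacy variable will be performed". It also says that the odds ratios and confidence intervals of the primary and sensitivity analyses "will be presented on the same graph to allow visual comparison of the robustness of the results".

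ASAS40 inherits the same step. Step 4 of the reference-based procedure in Section 8.2.2.2 reads "For ASAS40, complete parts 5 and 6 from" Section 8.1.3.2, and Section 8.2.3 sends the ASAS40 multiple imputation to the same place. All of this is current body text, not the amendment log.

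**The concern.** The two steps contradict themselves. A programmer cannot both include Baseline and match the primary analysis, because the primary has no Baseline term.

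The choice affects the estimate. For a logistic model, the treatment odds ratio conditional on a prognostic covariate differs from the one without it, even under perfect randomisation and complete data, and it is usually further from 1. If the multiple-imputation row sits to the right of the primary row on the shared graph, the reader cannot tell how much comes from the missing-data assumption and how much from the extra covariate.

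The tipping point has a related problem. Section 8.1.3.3 runs it only if the primary analysis, without Baseline, is significant, and then searches for the tipping delta in a model with Baseline. The reported delta is not the one at which a model with the primary's covariates loses significance.

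For ASAS40, the primary variable for Canada (Section 2.2.1.1), the covariate cannot be identified. The response combines patient global assessment, total spinal pain, BASFI and the mean of BASDAI questions 5 and 6, and no single baseline value belongs to it.

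**Working it through.** **Covariates in each analysis, side by side**

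| Analysis | Section | Treatment, region, MRI/CRP | Baseline |
|---|---|---|---|
| Primary composite | 8.1.2 | yes | no |
| Observed data at Week 52 | 8.1.3.1 | yes | no |
| Multiple imputation | 8.1.3.2, step 5 | yes | yes |
| Tipping point | 8.1.3.3, step 4 | yes | yes |
| Observed case | 8.1.3.4 | yes | no |

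**The plan's own figure first.** Inputs from Section 2.4: response 40% and 20%, 150 per arm, two-sided 0.05, power 95%. With a mean proportion of 0.30, the null standard error is √(2 × 0.3 × 0.7 / 150) = 0.0529 and the alternative standard error is √((0.4 × 0.6 + 0.2 × 0.8) / 150) = 0.0516. Power = Φ((0.2 − 1.96 × 0.0529) / 0.0516) = 96.9%. With a continuity correction it is 95.9%, and by Fisher's exact test 96.0%. The stated 95% is reproduced and is not in dispute.

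**Odds ratio without Baseline, complete data.** (0.4 / 0.6) / (0.2 / 0.8) = 2.67. The standard error of its log is √(1 / (150 × 0.4 × 0.6) + 1 / (150 × 0.2 × 0.8)) = √(1/36 + 1/24) = 0.264. The expected 95% interval is exp(0.981 ± 1.96 × 0.264) = 1.59 to 4.47, and z = 0.981 / 0.264 = 3.72.

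**Odds ratio with Baseline, the same complete data.** Take a standardised normal baseline x and logit P(response) = α_t + γx in arm t, where γ is the log of the baseline odds ratio per SD. Solve numerically for α_t so that the average response stays at 40% and 20%. The conditional treatment odds ratio is exp(α_CZP − α_placebo). Region and MRI/CRP are left out of both models for simplicity.

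| Assumed baseline OR per SD | Treatment OR given Baseline | Change from 2.67 | Expected 95% CI | z |
|---|---|---|---|---|
| 1 (not prognostic) | 2.67 | none | 1.59 to 4.47 | 3.72 |
| 1.5 | 2.75 | +3% | 1.63 to 4.66 | 3.77 |
| 2 | 2.92 | +9% | 1.70 to 5.03 | 3.86 |
| 2.5 | 3.11 | +17% | 1.77 to 5.45 | 3.96 |
| 3 | 3.30 | +24% | 1.85 to 5.88 | 4.04 |
| 4 | 3.66 | +37% | 1.99 to 6.74 | 4.17 |

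**Single trials.** In 1,000 simulated complete-data trials per scenario, both models were fitted to the same data. The ratio of the adjusted to the unadjusted odds ratio had medians of 1.03, 1.09 and 1.25 for baseline odds ratios of 1.5, 2 and 3 per SD. The central 95% ranges were 0.94–1.18, 0.93–1.33 and 0.97–1.69. In one trial the covariate alone can therefore move the row visibly, usually but not always away from 1.

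**The case against.** The strongest reply is that the rows were never going to match exactly. The primary counts discontinuation as failure. Multiple imputation discards post-discontinuation data and assumes missing at random. The observed-data row admits open-label treatment, and the observed-case row drops subjects. Even at delta 0 the tipping-point analysis is an imputation analysis, not the primary composite. Against an expected interval of 1.59 to 4.47, a shift of a few percent is secondary. All of this is true, but those differences are the intended ones. The covariate is an unintended further difference, and the plan describes it as no difference at all. The graph point is also clearest for multiple imputation, because step 6 of Section 8.1.3.3 puts the tipping-point results in a table.

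Three stronger readings are tempting and are not supported.

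- A reader might infer that baseline ASDAS is strongly prognostic by construction: the lowest score is 0.579 × ln 3 = 0.636, so nobody starting below 2.636 can fall by 2.0. Section 8.1.1 also counts the lowest possible score as a response, so such subjects can respond. The SAP gives no baseline distribution from which to size the effect.
- A reader might infer that the primary model is deficient because it forgoes precision. Treatment plus the two stratification factors is a legitimate model, and the planned power is reached without Baseline.
- A reader might want Baseline added to the primary model. Sections 2.2.1.3 and 8.4 refer to double-blind outputs already produced, Section 8.1.1 refers to the Week 52 interim lock analyses, and Section 4.3 releases treatment codes to the reporting team at that lock. The addition would change the confirmatory test after unblinding.

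**Conclusion.** The point stands as an internal contradiction with a real but bounded consequence. The multiple-imputation and tipping-point models differ from the primary by one covariate while claiming to match it, and the ASAS40 analyses that use the same step have no defined Baseline at all.

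On complete data at the planned rates, the mismatch alone takes the odds ratio from 2.67 to roughly 2.75–3.11 under moderate baseline effects, and to 3.66 under a strong one. The expected z statistic rises from 3.72 to between 3.77 and 4.17, so the tipping-point search would usually start from somewhat stronger evidence than a model with the primary's covariates would give. If Baseline is not prognostic, nothing moves. The sizes rest on assumed effects and on a logistic model with a normal baseline. Reading Baseline as baseline ASDAS is an inference, because that is the variable being imputed.

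The primary test, its stated power, its type I error and the testing hierarchy are untouched. What is weakened is the robustness evidence placed beside the primary result.

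**What to change.** Leave Section 8.1.2 as it is. In Section 8.1.3.2 step 5 and Section 8.1.3.3 step 4, delete the addition of Baseline as a covariate; the remaining claim to follow the primary analysis then becomes true. The ASAS40 analyses that import step 5 through Sections 8.2.2.2 and 8.2.3 are corrected by the same edit.

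Because Week 52 outputs exist, record which model produced the multiple-imputation and tipping-point results, and rerun those that included Baseline.

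If a baseline-adjusted view is wanted, make it a separately labelled supplementary analysis, name the baseline variable for each endpoint, and apply it to every row, the primary included.

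The cost is two short wording changes and one covariate removed from existing code. No new data are needed and the confirmatory analysis does not change.

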### 8.1.3.3 Tipping point analysis

In this analysis, various assumptions will be made about average outcomes among the subsets of subjects who prematurely discontinued double-blind study treatment and hence have a monotone missing data pattern. Various “delta adjustments” will be made to the assumed responses among missing ASDAS data in each treatment arm with varying degrees of plausibility (O’Kelly, 2014) prior to classification of the composite endpoint ASDAS-MI. The goal of the tipping point analysis is to identify assumptions about the missing data under which the conclusions from the logistical regression change, i.e., under which there is no longer evidence of a treatment effect. Then, the plausibility of such assumptions will be discussed.

Since the tipping point analysis is to find out how much of a change is required to “tip” the result from statistically significant at the  $\alpha=0.05$  level to not statistically significant, it will not be performed if the primary endpoint analysis is not statistically significant ( $p\text{-value} \leq 0.05$ ) at the onset.

1. Steps 1 and 2 from [Section 8.1.3.2](#) will be completed followed by steps 2-6 as shown below. Note that as described in [Section 8.1.3.2](#), part 1, ASDAS data collected after the discontinuation of double-blind study treatment will be treated as missing and then imputed using the methods described. Hence, all open-label period data is excluded from this analysis.

2. The remaining monotone missing data for all subjects will be imputed by treatment group. A regression with ASDAS measurement from the previous visit(s), MRI/CRP classification and region as explanatory variables will be used to impute the missing data including a MNAR mechanism under different assumptions. For subjects randomized to the Placebo treatment group, a MNAR mechanism will be assumed by using a specified negative shift to decrease the ASDAS parameter values prior to classifying the subject according to the ASDAS-MI endpoint. For subjects randomized to the CZP treatment group, a MNAR mechanism will be assumed by using specified positive shift parameters to increase imputed ASDAS values prior to classifying the subjects according to the ASDAS-MI endpoint. The size of the shift in the CZP or PBO treatment group will be investigated to determine at what point the analysis leads to a non-significant result.

As it is the raw ASDAS scores being imputed, the shift size (delta) will start with 0, 0.1, 0.2, 0.3, 0.4, 0.6, 0.8, 1.0, 1.2, 1.4, 1.6 and 1.8. Further values for delta may be investigated depending on the results obtained in order to determine the point at which the results are no longer significant.

When tipping point analyses is applied to ASAS40 response, the imputation will be done on the raw components before assessing the imputed results for ASAS40 response. The same delta shifts (0, 0.1, 0.2, 0.3, 0.4, 0.6, 0.8, 1.0, 1.2, 1.4, 1.6 and 1.8) will be investigated applied to the raw components (each of which are on a scale from 0 to 10) prior to calculating ASAS40 response. Further values for delta may be investigated depending on the results obtained.

This will be done once for each of the 100 datasets. The same delta value will be assumed for all visits.

3. The ASDAS change from Baseline to Week 52 will be calculated using the complete datasets (with no missing data) and categorized as: ASDAS- MI or not ASDAS-MI.
4. For each of the 100 imputed datasets (identified by `_imputation_` variable), the odds ratio of the treatment comparison and corresponding 95% CI for ASDAS-MI responder rates at Week 52 based on the observed data will be estimated using a logistic regression model with factors of treatment group, region, and MRI/CRP classification (MRI+/CRP+; MRI+/CRP-; MRI-/CRP+) and Baseline as a covariate in the same manner as the primary endpoint analysis.
5. The results from these analyses will be combined into a single inference using SAS PROC MIANALYZE. The parameter estimate and 95% CIs will be back transformed (using the exponential function) to give the odds ratio and CI for the CZP vs PBO comparison. This will be presented alongside the p-value from the proc mianalyze.
6. Steps 2 through 5 will be repeated using different values for the shift parameter as specified in step 2. Following the final Step 5, for each value of delta, the odds ratios, CIs and p-values will be presented in a single table with the associated delta value which was applied in the analysis.

